1.0 BACKGROUND AND RATIONALE

1.1 Non-Small Cell Lung Cancer (NSCLC)

Lung cancer remains the leading cause of cancer-related death, with an estimated 1.6 million deaths per year ¹. In the United States, the American Cancer Society estimates that there will be approximately 250,000 new cases of lung cancer and 158,000 deaths in 2018 ². Approximately 85% of patients with lung cancer have a group of histological subtypes, collectively known as non-small cell lung cancer (NSCLC) ³. The majority of patients with NSCLC present with stage IV disease due to distant metastases or malignant pleural effusion and are treated with palliative intent ⁴. Even among patients undergoing surgery with curative intent, a high percentage of tumors recur, with 5-year overall survival (OS) ranging from 83% in stage IA to 36% in stage IIIA ⁵. Patients with metastatic NSCLC and no targetable oncogenic alterations usually have a poor prognosis, with low responses to the initial platinum-based chemotherapy and virtually universal relapse ⁶. Immune checkpoint blockers (ICBs) have revolutionized the treatment of NSCLC, with the three approved drugs (nivolumab, pembrolizumab and atezolizumab) being more effective than docetaxel in randomized clinical trials ⁷⁻¹⁰. Nevertheless, the benefit is restricted to a small percentage of patients, with objective response rates of less than 20% and median progression-free survival (PFS) ranging from 2.3 to 3.9 months.

1.2 Atezolizumab

Under normal physiologic conditions, the immune checkpoint molecules maintain self-tolerance preventing autoimmunity and limiting collateral damage to the normal tissues during response to infections ^{11,12}. Cancer cells however, may co-opt these molecules to evade immune destruction. Programmed death 1 (PD-1), one of the key checkpoint molecules, may bind to two ligands, PD-L1/PD-L2. PD-L1 is an extracellular protein that downregulates immune responses primarily in peripheral tissues through binding to its two receptors PD-1 and B7.1. PD-1 is an inhibitory receptor expressed on T cells following T-cell activation, which is sustained in states of chronic stimulation such as in chronic infection or cancer ^{13,14}. Binding of PD-L1 with PD-1 inhibits T-cell proliferation, cytokine production, and cytolytic activity, leading to the functional inactivation or exhaustion of T cells. B7.1 is a molecule expressed on antigen-presenting cells and activated T cells. PD-L1 binding to B7.1 on T cells and antigen-presenting cells can mediate downregulation of immune responses, including inhibition of T-cell activation and cytokine production ^{15,16}. Overexpression of PD-L1 on tumor cells and the tumor microenvironment has been reported to prevent anti-tumor immunity, resulting in immune evasion ¹⁷. Therefore, interruption of the PD-L1/PD-1 pathway represents an attractive strategy to reinvigorate tumor-specific T-cell immunity. Atezolizumab is a humanized IgG1 monoclonal antibody against PD-L1 ¹⁸. Direct targeting of PD-L1 leaves the PD-L2-PD-1 interaction intact, potentially avoiding effects on immune homeostasis. Atezolizumab is approved in the United States metastatic NSCLC that has progressed during or following treatment with a platinum-containing regimen.

1.3 Ramucirumab

Vascular endothelial growth factor (VEGF) and VEGF receptor-2 (VEGFR-2)-mediated signaling and angiogenesis contribute to the pathogenesis of lung cancer. In patients with lung cancer, circulating VEGF levels are associated with increased tumor aggressiveness and reduced survival¹⁹. Furthermore, high levels of VEGF in preclinical models reduced the T cell progenitors in the thymus²⁰, and exposure to VEGF led to decreased number, activity and cytotoxic activity of T cells *ex vivo* in a VEGFR-2 dependent mechanism²¹. Blocking VEGF receptor-mediated signaling abrogated VEGF's suppressive effects on T-cells in preclinical models and VEGFR-2 inhibition reduced tumor growth in lung adenocarcinoma animal studies^{22,23}. Ramucirumab, a human IgG1 monoclonal antibody against VEGFR-2, prevents ligand binding and receptor-mediated pathway activation in endothelial cells and is currently indicated for the treatment of multiple malignancies including gastric and gastric-esophageal adenocarcinomas progressing after platinum-containing therapy and in combination with docetaxel in metastatic NSCLC with disease progression on or after platinum-based chemotherapy²⁴. Ramucirumab in combination with docetaxel has demonstrated improved response rates and PFS in NSCLC patients compared to docetaxel alone²⁵. In early phase studies, ramucirumab in combination with ICBs has shown promising results in ICB-naïve patients²⁶.

1.4 Rationale

Although ICBs have changed advanced NSCLC treatment, only a small percentage achieve a sustained benefit. Furthermore, efficacy from additional therapy is limited²⁷. While the lack of response to ICBs is likely multifactorial, an important factor in achieving a response with anti-PD-1/PD-L1 blockade is the presence of T cells entering the tumor to kill the tumor cells once their defense is removed. Unfortunately, tumors often inhibit T-cell trafficking to the tumor via vascular endothelial growth factor (VEGF)-mediated down-regulation of important adhesion molecules on tumor-associated blood vessels and failure to respond to ICBs has been associated with decreased tumor-infiltrating immune cells²⁸²⁹. Inhibition of VEGF-VEGFR-2 signaling results in increased T-cell invasion into the tumor^{28,30,31}, and preclinical models have demonstrated a synergistic effect of blocking both tumor-associated immunosuppression and angiogenesis^{30,32,33}. Furthermore, inhibition of VEGF receptor mediated signaling decreased PD-1 expression on cytotoxic T-cells, suggesting that inhibition of this pathway may enhance T-cell function in the tumor microenvironment³⁴. Indeed, use of immunotherapy and anti-angiogenesis therapy in melanoma also increased CD8+ T-cell infiltration in tumors³¹. Together, this data suggests that combining ramucirumab with immunotherapy in NSCLC patients who have previously received ICBs may be more effective than traditional therapy. We propose a pilot study to test the combination of ramucirumab and atezolizumab in patients with advanced-stage NSCLC patients previously treated with ICB.

1.5 Correlative Studies Background

Despite the widespread use of PD-1/PD-L1 antagonists for patients with NSCLC, the exact molecular mechanisms that mediate disease response remain poorly understood³⁵. It is clear that PD-1-directed therapies induce proliferation and increase the functional activity

of CD8+ T-cells in the periphery of patients ³⁶⁻³⁸, but despite this, the majority of patients will not derive meaningful benefit from this class of agents, and responses are often not durable. Blunting tumor angiogenesis in order to remodel the tumor microenvironment is an attractive combinatorial approach to synergize with standard immunoncology agents ³⁹. Increased VEGF expression is known to suppress the maturation of antigen-presenting dendritic cells and inhibit lymphocyte tracking into tumor tissues, which can limit the effectiveness of an antitumor adaptive immune response ⁴⁰. We hypothesize that the addition of ramucirumab will augment the clinical activity of atezolizumab, and in order to evaluate the exact mechanism of action of the combination, we propose a comprehensive analysis of paired peripheral blood samples collected longitudinally during this study. We will evaluate whether the combination of atezolizumab and ramucirumab (a) alters populations of circulating monocytes and myeloid derived suppressor cells, (b) increases the number and affects the phenotype of circulating NK cells, effector CD8+ and effector CD4+ T-cell subsets, (c) results in the generation of durable populations of memory CD8+ and CD4+ T-cells and (d) alters the ratio of circulating regulatory T-cells to effector CD8+ cells. We will utilize mass cytometry (CyTOF) for these analyses, a high dimensional technique that allows the assessment of ~40 individual markers using metal labeled antibodies to enable deep profiling of selected phenotypic and functional markers on individual cells as well as unique statistical analyses to simplify the interpretation of complex relationships of large numbers of cells ⁴¹⁻⁴³. We will collect and cryopreserve peripheral blood mononuclear cells prior to combination atezolizumab/ramucirumab therapy and again at the time of first radiographic assessment. Analyses will be completed in a batched fashion using an established mass cytometry panel at the The Andrew M. and Jane M. Bursky Center for Human Immunology & Immunotherapy Programs (CHiPs) at Washington University School of Medicine at the conclusion of study procedures to correlate immune profiles with clinical response. Patients will also undergo repeated biopsy to evaluate the differences in immune cell infiltrates between baseline and after two cycles of treatment.

1.6 Amendment #3 Study Continuation

1.6.1 Synopsis

The primary objective of the RamAtezo trial is to determine the overall response rate for the combination of ramucirumab and atezolizumab in patients with NSCLC previously treated with immune checkpoint blocker. This is an unmet need where there are few treatment options for patients after tumor progression on immune checkpoint blockers, particularly when used in combination with platinum-based doublet in the first-line setting.

The study design uses a Simon's two-stager MiniMax design where 12 patients are enrolled into the stage I. In case of one or more responses, the study will accrue 9 more patients, with a total of 4 responders indicating the preliminary evidence of efficacy.

Although there were no responses among the initial 12 patients, 8 patients had tumor reduction from baseline, including patient reaching 27% reduction, only 3% below the threshold for the RECIST criteria for response. Furthermore, the treatment has been well tolerated and 3 out of the 12 patients (25%) are still on treatment with progression-free survival higher than 6 months.

Therefore, we believe that the study should continue with the accrual of the additional 9 patients with the primary endpoint remaining the overall response rate. In this case, the Minimax design will be replaced by a simple enrollment of 21 patients.

2.0 OBJECTIVES

2.1 Primary Objective

To determine the overall response rate (ORR) for the combination of ramucirumab and atezolizumab in patients with NSCLC who have previously received an ICB.

2.2 Secondary Objectives

1. To determine the overall survival (OS) for the combination of ramucirumab and atezolizumab in patients with NSCLC who have previously received an ICB.
2. To determine the progression-free survival (PFS) for the combination of ramucirumab and atezolizumab in patients with NSCLC who have previously received an ICB.
3. To determine clinical benefit rate (CBR) for the combination of ramucirumab and atezolizumab in patients with NSCLC who have previously received an ICB. CBR is defined as the percentage of patients who have achieved responses or stable disease.
4. To evaluate toxicity and tolerability of this combination as measured by NCI-CTCAE version 5.0.

2.3 Exploratory Objectives

1. To explore the relationship of the immunophenotype of peripheral blood immune cells and response to combined therapy.
2. To explore the changes in tumor immune cell infiltrate after treatment and relationship with response.

3.0 PATIENT SELECTION

3.1 Inclusion Criteria

1. Histologically or cytologically confirmed squamous or non-squamous non-small cell lung cancer. Patients with known EGFR or ALK mutations are eligible only if they have received at least one line of targeted therapy for these mutations.

2. Availability of archival biopsy tissue or willingness to undergo a “baseline” biopsy prior to initiation of the trial for biomarker analysis, including PD-L1 by IHC.

Note: Results of PD-L1 testing are not required for enrollment.

3. Measurable disease defined as lesions that can be accurately measured in at least one dimension (longest diameter to be recorded) as ≥ 10 mm with CT scan, as ≥ 20 mm by chest x-ray, or ≥ 10 mm with calipers by clinical exam.
4. Prior use of an immune checkpoint blocker alone or in combination therapy.
5. At least 18 years of age.
6. ECOG performance status ≤ 1 (see Appendix A)
7. Normal bone marrow and organ function as defined below:
 - a. Absolute neutrophil count $\geq 1,500$ /cumm
 - b. Platelets $\geq 100,000$ /cumm
 - c. Hemoglobin ≥ 9.0 g/dL
 - d. Total bilirubin ≤ 1.5 x ULN
 - e. AST(SGOT)/ALT(SGPT) ≤ 3.0 x ULN or 5.0 x ULN in the setting of liver metastasis
 - f. Serum creatinine ≤ 1.5 x ULN or CrCl ≥ 40 mL/min. if serum creatinine is >1.5 times the ULN, a 24-hour urine collection to calculate creatinine clearance must be performed
8. Adequate coagulation function as defined by:
 - a. INR ≤ 1.5
 - b. PTT/aPTT < 1.5 x ULN

Note: Patients on full-dose anticoagulation must be on a stable dose (minimum duration 14 days) of oral anticoagulant or low molecular weight heparin (LMWH). If receiving warfarin, the patient must have an INR ≤ 3.0 . For heparin and LMWH there should be no active bleeding (that is, no bleeding within 14 days prior to first dose of protocol therapy) or pathological condition present that carries a high risk of bleeding (for example, tumor involving major vessels or known varices).

9. Urinary protein $\leq 1+$ on dipstick or routine urinalysis; if urine dipstick or routine analysis is $\geq 2+$, a 24-hour urine collection for protein must demonstrate < 1 g of protein in 24 hours to allow participation
10. Women of childbearing potential and men must agree to use adequate contraception (hormonal or barrier method of birth control, abstinence) prior to study entry and for the duration of study participation. Should a woman become pregnant or suspect she is pregnant while participating in this study, she must inform her treating physician immediately.

11. Ability to understand and willingness to sign an IRB approved written informed consent document (or that of legally authorized representative, if applicable).

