6.2 Dose Modifications for Atezolizumab

Atezolizumab dose reduction is not allowed. However, study treatment may be temporarily

suspended in patients experiencing toxicity considered to be related to study treatment for up to 60 days after the last dose if they experience toxicity that require a dose to be withheld. If atezolizumab is withheld because of toxicity for > 60 days after the last dose, then the patient will be discontinued from atezolizumab treatment and will be followed for safety and efficacy.

Recommendations for dosage modifications are provided in the table below:

Adverse Reaction	Severity (by CTCAE Grade)	Dosage Modifications
Pneumonitis	2	Withhold dose until grade 1 or resolved and corticosteroid dose \leq 10 mg/day (or equivalent)
	3 or 4	Permanently discontinue
Hepatitis	AST or ALT 3-5 x ULN or total bilirubin 1.5-3 x ULN	Withhold dose until grade 1 or resolved and corticosteroid dose \leq 10 mg/day (or equivalent)
	AST or ALT > 5 x ULN or total bilirubin > 3 x ULN	Permanently discontinue
Colitis or diarrhea	2 or 3	Withhold dose until grade 1 or resolved and corticosteroid dose \leq 10 mg/day (or equivalent)
	4	Permanently discontinue
Endocrinopathies (including but not limited to hypophysitis, adrenal insufficiency, hyperthyroidism, and type 1 diabetes mellitus)	2, 3, or 4	Withhold dose until grade 1 or resolved and clinically stable on hormone replacement therapy
Other immune-mediated adverse reactions involving a major organ	3	Withhold dose until grade 1 or resolved and corticosteroid dose \leq 10 mg/day (or equivalent)
	4	Permanently discontinue
Infections	3 or 4	Withhold dose until grade 1 or resolved
Infusion-related reactions	1 or 2	Interrupt or slow the rate of infusion
	3 or 4	Permanently discontinue
Persistent grade 2 or 3 adverse reaction (excluding endocrinopathies)	2 or 3 that does not recover to 0 or 1 within 60 days after last dose	Permanently discontinue
Inability to taper	Inability to	Permanently discontinue

corticosteroid	reduce to ≤ 10 mg/day (or equivalent) within 60 days after last dose	
Recurrent grade 3 or 4 adverse reaction	Recurrent grade 3 or 4	Permanently discontinue

Dose interruptions for reasons other than toxicity (e.g., surgical procedures) may be allowed, with PI approval. The PI will determine the acceptable length of interruption.

Patients who discontinue atezolizumab must come off study.

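### Apart from pneumonitis, no criterion clearly excludes a patient whose resolved immune-mediated event on a prior checkpoint blocker would permanently stop atezolizumab under Section 6.2

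*Combined protocol and SAP*

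**What the plan says.** Section 3.1, item 4 makes earlier checkpoint blockade a condition of entry: "Prior use of an immune checkpoint blocker alone or in combination therapy". It does not ask why the drug was stopped or what toxicity it caused. No criterion bars earlier atezolizumab, which Section 1.1 names among the approved agents, so the prior drug may be the study drug.

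Section 6.2 introduces its table with "Recommendations for dosage modifications are provided in the table below". The immune-mediated events for which that table permanently discontinues atezolizumab include:

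- pneumonitis of grade 3 or 4;
- hepatitis with "AST or ALT > 5 x ULN or total bilirubin > 3 x ULN";
- colitis or diarrhea of grade 4;
- "Other immune-mediated adverse reactions involving a major organ", at grade 4;
- "Recurrent grade 3 or 4 adverse reaction".

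Endocrinopathies are treated differently, even at grade 4: "Withhold dose until grade 1 or resolved and clinically stable on hormone replacement therapy".

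Section 3.2, item 12 excludes any history of pneumonitis and says that drug-induced disease counts. Item 11 excludes a history of autoimmune disease through an open-ended list and does not mention drug-induced events.

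**The concern.** Every enrolled patient is being re-exposed to checkpoint blockade. The protocol has its own view of which events should end exposure to atezolizumab for good, but the entry criteria do not clearly apply that view to the same events on the earlier drug. A patient with a resolved hepatitis above the Section 6.2 limit could be enrolled by following the criteria exactly. A patient who had the same hepatitis on study would, under the table, not receive atezolizumab again.

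What is at stake is patient safety. The primary response analysis is barely touched.

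A secondary wording point concerns exclusion 1. It does not list systemic corticosteroids and states no dose, yet its note exempts brief low-dose use, which suggests that heavier use was meant to be barred. Individual investigators at the one center may read it differently.

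**Working it through.** **Criteria against the permanent-discontinuation rows.** The plan gives no figure to reproduce. The check is whether each event, now resolved, is clearly excluded when it occurred on the prior drug.

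| Section 6.2 event | Criterion that might catch it | Clearly excluded? |
|---|---|---|
| Pneumonitis, grade 3-4 | Exclusion 12: any history, drug-induced included | Yes |
| Hepatitis above the stop limit | Inclusion 7 tests current liver values only; exclusion 16 needs clinically significant liver disease | No |
| Colitis or diarrhea, grade 4 | Exclusion 9 (perforation risk, 6 months); exclusion 10 (severe GI bleeding, 3 months); exclusion 11 (names inflammatory bowel disease) | Not clearly |
| Other major organ, grade 4 | Exclusion 11, for example glomerulonephritis or Guillain-Barré syndrome | Not clearly |
| Recurrent grade 3-4 | None names recurrence | No, unless the event was pneumonitis |

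Exclusion 5 covers allergic reactions to checkpoint blockers. That is a different kind of event from organ toxicity.

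Exclusions 11 and 12 are adjacent. One says that drug-induced disease counts and the other is silent. A literal reader could therefore treat exclusion 11 as limited to primary autoimmune disease.

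Two further rows also end treatment: "2 or 3 that does not recover to 0 or 1 within 60 days after last dose", and failure to taper corticosteroids within the same 60 days. They are time limits for managing a patient on treatment, and they are left out here because as lifetime exclusions they would reach too far.

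**Illustrative size.** Section 1.6.1 gives 12 patients already treated and a total of 21, so 21 - 12 = 9 further patients were planned. Current accrual is not stated, so 6 and 3 remaining are shown as well. The share p of otherwise eligible candidates with such a history is not in the documents; 1% and 5% are assumptions.

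P(at least one admitted) = 1 - (1 - p)^m, if every such candidate is enrolled:

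- m = 9: 1 - 0.99^9 = 0.087; 1 - 0.95^9 = 0.370
- m = 6: 1 - 0.99^6 = 0.059; 1 - 0.95^6 = 0.265
- m = 3: 1 - 0.99^3 = 0.030; 1 - 0.95^3 = 0.143

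Expected number among 9: 9 x 0.01 = 0.09 to 9 x 0.05 = 0.45.

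Share of the pooled 21: 0.09/21 = 0.4% to 0.45/21 = 2.1%.

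Extra candidates needed to fill 9 places: 9/0.99 - 9 = 0.09 to 9/0.95 - 9 = 0.47.

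**The case against.** The strongest reply is that exclusion 11 already does much of this work. It concerns history, so resolved disease counts. Its list is open-ended, sets no limit by cause, and names bowel, nerve and kidney conditions. An investigator could fairly use it to decline a patient with immune-related colitis, nephritis or neuropathy. This stands: for those events the defect is unclear wording. It does not help with resolved hepatitis, and recurrence is not named anywhere.

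Second, the Section 6.2 table offers recommendations for on-study events and is not an eligibility standard. Enrolment is permitted, never compelled, and a careful investigator may decline. This also stands, and it limits how strongly the point can be put.

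Third, there are safeguards. Section 6.2 withholds atezolizumab at grade 2 colitis and at AST or ALT of 3-5 x ULN, below the levels at issue. The study calendar has a metabolic panel on Day 1 of every cycle, and a history and physical from Cycle 2 on. Section 5.5 lets the investigator remove a patient, and Section 13.0 provides ongoing toxicity monitoring. These can limit harm, but only after re-exposure. Section 1.6.1 reports good tolerability in the first 12 patients without saying whether any had such a history.

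A reader might also infer that the protocol calls for an entry limit of 10 mg/day on corticosteroids. It does not. That figure belongs to the rule for resuming after an on-study event ("Withhold dose until grade 1 or resolved and corticosteroid dose" at or below 10 mg/day). Section 5.3.2 bars named immunosuppressants during treatment but leaves systemic corticosteroids to the treating physician, so their absence from exclusion 1 may be deliberate. The unmatched bracket in exclusion 1 may be a drafting slip or an artifact of PDF reading.

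**Conclusion.** The point holds in a limited form: it is a cheap safety improvement, held with medium confidence. Apart from pneumonitis, the criteria do not clearly keep out a patient with a resolved event for which the protocol's own table would permanently stop atezolizumab. Hepatitis is the clearest case.

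Three stronger readings are not supported:

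- That severe prior immune toxicity is unaddressed. Exclusion 12 covers pneumonitis outright, and exclusion 11 may cover more.
- That 9% to 37% measures harm. It is a chance of admission under an assumed prevalence and assumes that every such candidate is enrolled; the documents give neither the frequency of such histories nor the risk of recurrence.
- That centers would apply the criteria differently. Section 14.2 describes a single-institution study, so at most individual investigators could differ.

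Ongoing toxicity at entry is a separate question, which this comparison of resolved events does not settle. The corticosteroid point is a wording clarification only.

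**What to change.** For patients not yet enrolled, add one item to Section 3.2:

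*Prior immune-mediated toxicity on an immune checkpoint blocker that was grade 4 colitis/diarrhea or grade 4 in another major organ (excluding endocrinopathy controlled on hormone replacement), hepatitis with AST/ALT > 5 x ULN or total bilirubin > 3 x ULN, or recurrent grade 3-4.*

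The thresholds come from Section 6.2. The endocrinopathy exception follows that table and fits the note to exclusion 11, which admits stable hypothyroidism and controlled type 1 diabetes.

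Separately, state in exclusion 1 whether systemic corticosteroids are meant to be covered and, if so, what low dose means. The number is for the investigator to choose. On-study use under Section 5.3.2 need not change.

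The cost is an eligibility amendment and the retrieval of prior toxicity records, possibly from another center. A few candidates may be turned away (0.09 to 0.47 on average to fill 9 places, under the assumed rates). Later patients would enter under slightly narrower criteria than the first 12, although all 21 are analyzed together; the 4-responder rule in Section 14.2 stays as it is. If accrual is complete, the change has no effect.
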